15. STATISTICAL CONSIDERATIONS

1. Study Design

This study will be a multi-institution, open-label, phase Ib/II clinical trial conducted in 2 parts: a Phase 1b part followed by a Simon's two-stage Phase 2 design. The study will assess the safety and efficacy of APR-246 in combination with azacitidine for the treatment of *TP53* mutant myeloid neoplasms. All patients will have pre-screening NGS on peripheral blood (PB) or bone marrow (BM) samples to determine *TP53* mutational status and therefore eligibility to participate in this study. A PB sample will be obtained prior to treatment for NGS by the central laboratory to evaluate baseline VAF and for serial analysis. The initial Phase 1b part will evaluate APR-246 administered with azacitidine. Cohorts of at least 3 evaluable patients will be enrolled using a modified 3 + 3 design. The MTD is defined as the dose level below which DLT is manifested in $\geq 33\%$ of the patients or at dose level 1 if DLT is manifested in $< 33\%$ of the patients.

Following completion of the Dose Finding Phase, we will conduct a dose expansion, whereby patients will be treated with APR-246 administered at the MTD with azacitidine on a 28 day cycle utilizing the same dosing schedule as in Phase 1b. All patients who complete at least one treatment cycle of APR-246 and azacitidine and who have at least one post-treatment clinical response assessment will be considered eligible for the efficacy-evaluable population and will be summarized for all efficacy variables. Patients who fail to complete one treatment cycle will also be considered efficacy-evaluable if they show clear evidence of clinically significant disease progression. Patients who are not efficacy-evaluable will be replaced. A Simon's two-stage minimax design will be applied, as follows:

Stage 1: Enroll a total of 24 evaluable patients at the MTD (including patients who were enrolled during the Phase 1 part of the study). If less than 6 of 24 patients achieve CR, then the study will be terminated early with the conclusion that the regimen does not warrant further investigation. If 6 or more patients achieve CR, then enrollment will be permitted to continue to Stage 2.

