Stage 2: Enroll 21 more evaluable patients for a total of 45. If less than 14 of 45 patients achieve CR, then there is insufficient evidence to support continued study of this treatment. If at least 14 of 45 patients achieve CR, then there is sufficient evidence to support further study of APR-246 in combination with azacitidine in Phase 3. Up to 39 additional evaluable patients will be treated at the level of the MTD in the

Phase 2 portion of the trial.

This rule has the following operating characteristics: 90% power, with $\alpha=0.05$ under the null hypothesis that the proportion of patients achieving CR is $\leq 20\%$ versus the alternative hypothesis that it is $\geq 40\%$. This design has a probability of early termination equal to 0.66 if the true CR rate is 20%.

2. Statistical Analysis Methods

Demographic and clinical variables for the study patients will be summarized using descriptive statistics (mean, standard deviation, median, inter-quartile range, range, frequency counts and percentages). Safety and efficacy data will be analyzed overall as well as separately for each dose cohort when appropriate.

3. Safety Analysis

This analysis will include all subjects who have received any protocol treatment, regardless of patient eligibility. The number (%) of subjects with adverse events, serious adverse events, and adverse events leading to treatment discontinuation will be reported. Adverse events summary will be reported by type and severity. Laboratory parameters will also be summarized using descriptive statistics.

4. Efficacy Analysis: ITT

This analysis will include all subjects who have received any protocol treatment, regardless of patient eligibility or duration of treatment. Those who have no response assessment data due to reasons such as drop out of the study, withdrawal consent, or lost to follow-up will be treated as non-responders for various response evaluations. The proportion of subjects achieving the primary endpoint will be summarized. A 95% exact binomial confidence interval of the proportion will also be provided for all participants treated at the MTD. In addition, a second analysis of evaluable subjects will be performed. Evaluable subjects are defined as those who complete at least 3 cycles of therapy and complete the first on treatment bone marrow biopsy and aspirate to evaluate study drug response.

Analyses of the following secondary endpoints will be performed as well:

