- i. Duration of response defined as the time between achieving response and progression of disease.
- ii. OS at 8 months
- iii. Proportion of subjects achieving hematological improvement (HI), partial response (PR), complete response (CR), and/or marrow CR (mCR) by the IWG 2006 criteria (see appendix B)
- iv. Proportion of subjects who obtain a response as defined by IWG 2006 criteria with a baseline *TP53* VAF $\geq 20\%$ versus $< 20\%$ or high versus low nuclear p53 protein expression

- v. Correlation of *TP53* VAF with nuclear p53 protein expression as determined by IHC
- vi. Proportion of subjects who achieve $\geq 50\%$ reduction in *TP53* VAF.
- vii. Progression free survival (PFS) and OS in clonal responders ($\geq 50\%$ reduction in *TP53* VAF) versus non-responders
- viii. Profile expression of genes related to p53-mediated signal transduction before and after APR-246 treatment
- ix. Profile ROS production before and after APR-246 treatment
- x. AML transformation according to World Health Organization (WHO) criteria
- xi. OS
- xii. LFS
- xiii. Determine recurrent gene mutations in *ASXL1*, *BCOR*, *BRAF*, *CALR*, *CBL*, *CEBPA*, *CSF3R*, *DNMT3A*, *ETV6*, *EZH2*, *GATA2*, *GNAS*, *IDH1*, *IDH2*, *JAK2*, *KIT*, *KRAS*, *MPL*, *NF1*, *NPM1*, *NRAS*, *PDGFRA*, *PDGFRB*, *PHF6*, *PTPN11*, *RAD21*, *RUNX1*, *SETBP1*, *SF3B1*, *SMC1A*, *SMC3*, *SRSF2*, *STAG2*, *STAT3*, *STAT5b*, *TET2*, *TP53*, *U2AF1*, *WT1*, and *ZRSR2* at study entry and serially throughout treatment to assess changes in somatic mutation landscape.

Preliminary data on the above endpoints will prove to be very useful for further investigation of this protocol's treatment. Such data will be summarized appropriately in an exploratory fashion. Both point estimates and 95% confidence intervals will be reported, if feasible. Time-to-event endpoints such as OS and LFS will be summarized using the Kaplan-Meier product-limit method.

16. Laboratory Correlates

Unless otherwise specified, all laboratory correlates will be performed in the laboratory of [name] or at Genoptix medical laboratory.

1. Mutation analyses

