Genoptix medical laboratory ([name]) will be the central laboratory for this study regarding molecular profiling. All patients will undergo baseline NGS for confirmation of *TP53* mutation, baseline *TP53* VAF, and identification of additional somatic mutations. These analyses will not impact enrollment into the clinical trial. Importantly, there will be serial evaluation following cycle 3 and cycle 6 where NGS will be repeated to evaluate for clonal reduction of *TP53* VAF as well as changes in the underlying mutational architecture of these patients. These analyses will be utilized for secondary endpoints #4-7. **For correlative genomic studies that will be performed at Genoptix medical laboratory, 2-3 mL of peripheral blood will be obtained in a standard Vacutainer tube with EDTA (purple top) as anticoagulant. If *TP53* mutation is only present on BM analysis at screening, serial NGS myeloid panel**

can be performed on bone marrow MNC. A FedEx shipping label will be included in the shipper box with a research specific requisition. Recurrent gene mutations of *ASXL1*, *BCOR*, *BRAF*, *CALR*, *CBL*, *CEBPA*, *CSF3R*, *DNMT3A*, *ETV6*, *EZH2*, *GATA2*, *GNAS*, *IDH1*, *IDH2*, *JAK2*, *KIT*, *KRAS*, *MPL*, *NF1*, *NPM1*, *NRAS*, *PDGFRA*, *PDGFRB*, *PHF6*, *PTPN11*, *RAD21*, *RUNX1*, *SETBP1*, *SF3B1*, *SMC1A*, *SMC3*, *SRSF2*, *STAG2*, *STAT3*, *STAT5b*, *TET2*, *TP53*, *U2AF1*, *WT1*, and *ZRSR2* will be evaluated at each NGS analysis. DNA and RNA will be isolated from BM-MNC by the Ficoll method following cycle 3 and cycle 6 and stored in the laboratory of [name]. In patients who become negative for *TP53* mutation by NGS (VAF sensitivity for this assay is 1% in patients with previously identified variants), we will perform PCR-based barcoding or digital droplet PCR to identify rare variants in an effort to determine the depth of remission induced by treatment with APR-246 and azacitidine.

2. Immunohistochemistry for p53 expression

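### The PFS and OS comparison by TP53 clonal response uses a status known only after cycle 3 or 6, with no landmark, no responder-defining visit and no single analysis set

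*Combined protocol and SAP*

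**What the plan says.** Section 15.4 vii (also Section 3.2.6 and the synopsis) lists "Progression free survival (PFS) and OS in clonal responders" versus non-responders. It is the endpoint that answers objective 1.3.7, whether clonal suppression correlates with outcome.

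**When status is known.** Section 16.1 states that "there will be serial evaluation following cycle 3 and cycle 6 where NGS will be repeated to evaluate for clonal reduction", and adds: "These analyses will be utilized for secondary endpoints #4-7". The comparison falls inside that range in both the Section 15.4 list (vii) and the Section 3.2 list (3.2.6). Section 13 puts the samples at C3D22 and C6D22, then every 3 cycles in continuation. It also provides for NGS at end of treatment, where feasible.

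**Method.** "Time-to-event endpoints such as OS and LFS will be summarized using the Kaplan-Meier product-limit method". Nothing further is specified for vii.

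**Analysis set.** Three statements compete:
- The secondary list stands under the ITT heading of Section 15.4, which covers everyone treated.
- It directly follows a second analysis: "Evaluable subjects are defined as those who complete at least 3 cycles of therapy" and have the first on-treatment marrow.
- Section 15.1 says that patients with one cycle and one assessment "will be considered eligible for the efficacy-evaluable population and will be summarized for all efficacy variables".

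**Missing assessments.** The text under the ITT heading provides that some patients "will be treated as non-responders for various response evaluations". It identifies this group as follows: "Those who have no response assessment data due to reasons such as drop out of the study, withdrawal consent, or lost to follow-up".

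**The concern.** A patient can be called a clonal responder only after living long enough to be sampled. If survival is counted from the start of treatment and the groups are formed by later status, responders carry time in which they could not have died. The size of this guaranteed-time effect depends on choices that the plan leaves open: which visit counts, and where patients without a VAF go. The same null data could then show no difference or a sizeable advantage for responders. The study is open-label, and those choices could be made after the data are seen. The result would be read as evidence on whether clearing the TP53 clone predicts benefit.

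**Working it through.** **Plan's own figure.** None is given for vii. The one stated calculation, the two-stage CR design, reproduces (alpha 0.048, power 0.900, early termination 0.656) and is not involved here.

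**Inputs from the documents.** C3D22 = 2×28+22 = day 78 (78/30.4375 = 2.563 months). C6D22 = 5×28+22 = day 162 (5.32 months). N = 45. Median OS 5-9 months, best estimate 8 (Section 2.2, historical).

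**Assumptions not in the documents.** Exponential times; no true association; 30-50% response at C3; 30% of C3 non-responders converting at C6; 24-month follow-up; median PFS 4-6 months.

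**Deaths before C3D22.** 1 − 0.5^(2.563/median) = 0.299, 0.199 and 0.179 at medians of 5, 8 and 9 months.

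**Kaplan-Meier illustration** (8-month median, 30% response, C3 status only, early deaths placed with non-responders):
- Survival to day 78: 0.801.
- Responders at 8 months: 0.5/0.801 = 0.624.
- Responder share: 0.3×0.801 = 0.240.
- Non-responders at 8 months: (0.5 − 0.240×0.624)/0.760 = 0.461.

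The curves read 62% against 46% when the truth is 50% in everyone.

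**OS, simulated null trials, 8-month median (median Cox HR):**

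| Handling | 30% at C3 | 50% at C3 |
|---|---|---|
| Unassessed left out, C3 only | about 1.0 | about 1.0 |
| Unassessed left out, C3 or C6 | 0.83 | 0.86 |
| Early deaths as non-responders, C3 only | 0.73 | 0.65 |
| Early deaths as non-responders, C3 or C6 | 0.57 | 0.52 |
| Day-89 landmark, C3 status | 1.01 | 1.00 |

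Repeat runs differ by about 0.01, and using n=51 changes the HRs by at most 0.01.

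**Sensitivity, OS:**
- Unassessed left out, C6 counted, medians 5-9 months: 0.92-0.96, 0.85-0.91 and 0.79-0.86 at 10%, 20% and 30% conversion.
- Early deaths as non-responders, medians 5-9 months: 0.57-0.75 (C3 only) and about 0.45-0.59 (C3 or C6).
- The same handling with half of the early deaths left unclassified: 0.56-0.86. With 15-25% of them having a responding end-of-treatment VAF: 0.54-0.97.
- A landmark at C3 does not help if C6 responses still define the groups. With conversion at C6 set equal to the C3 rate, it gives 0.82 (30%) and 0.75 (50%).

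**PFS** (medians 4-6 months, 30-50% response at C3, unassessed early events counted as non-response). The answer turns on how many early events come with a VAF; those that do are assumed to respond at the same rate:

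| Early events with a VAF | C3 only | C3 or C6 |
|---|---|---|
| None | 0.52-0.70 | 0.42-0.53 |
| Half | 0.73-0.85 | 0.58-0.63 |
| 80% | 0.89-0.96 | 0.66-0.71 |
| All | about 1.0 | 0.70-0.79 |

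**The case against.** **The plan does not say that early deaths are non-responders.** A reader might infer it from the ITT rule. That rule concerns response evaluations and names drop-out, withdrawal and loss to follow-up. It does not name death or VAF, although its list of reasons is open-ended. The objection stands: the larger OS figures are conditional. It does not remove the problem, because counting C6 responses biases the comparison even when patients without a C3 VAF are left out.

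**A set is arguably assigned.** The ITT heading covers the list, and Section 15.1 claims all efficacy variables for the efficacy-evaluable set. It would be wrong to say that the plan is silent. The accurate statement is that the passages compete and none is fixed for vii.

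**Early progressors often have a VAF.** Progression found at C3D22 comes with that visit's NGS, and patients who stop earlier have an end-of-treatment sample if feasible. This also stands: a PFS hazard ratio of 0.52-0.70 is the extreme, not the expectation.

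**No Cox model or test is planned, and the analysis is exploratory.** True, and it limits the severity. But the planned Kaplan-Meier curves show the same distortion, and an exploratory label does not correct a structural bias.

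**Conclusion.** The concern holds in a conditional form. Endpoint vii forms its groups by post-baseline status without a landmark, time-dependent handling, a responder-defining visit, a time origin or one settled analysis set.

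For OS, the bias is nil if only C3 status counts and unassessed patients are left out. It is modest (about 0.82-0.86 at an 8-month median) if C6 responses count, and larger only if early deaths are also placed with non-responders. For PFS it runs from about 0.52-0.70 to about 1.0 with C3 status only, according to how many early events have a VAF. All sizes rest on the assumed response and conversion rates, exponential times and follow-up.

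PFS is also incompletely defined. IWG 2006 supplies progression, but the handling of death, the time origin and censoring are not stated. Off-treatment follow-up (Sections 8 and 13) records AML transformation and survival, not progression.

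A reader might infer that the trial's main conclusion is at risk. It is not: the CR rule does not use this comparison, and no test of vii is planned. Severity is low to moderate, and the correction is worth making because it is cheap.

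**What to change.** In Section 15.4 vii, name one analysis set and state:

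- Clonal response is classified by the VAF at C3D22. One landmark day applies to all patients, counted from cycle 1 day 1: nominal day 78 plus the 7-working-day window (up to 11 calendar days), about day 89. A VAF obtained after that day does not count. A fixed day is needed because Section 10.3 requires discontinuation only for delays over 28 days, so actual C3D22 dates will vary.
- Only patients alive (for PFS, alive and progression-free) with a post-baseline VAF by that day are compared, and PFS and OS are counted from it.
- Patients without a VAF are not assigned to the non-responders; their number and the reasons are reported.
- Later VAF responses enter, if at all, only as a time-dependent covariate.
- PFS events are IWG 2006 progression or death. Censoring is stated for patients who stop treatment without progression or start new therapy.
- One time origin is given for the curves of all patients, since Phase 1b patients start drug at day −14 and Phase 2 patients at day 1.

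**Cost.** Wording only; no new samples. Deaths before day 89 (2.924 months) are 1 − 0.5^(2.924/median) = 33%, 22% and 20% at medians of 5, 8 and 9 months, which leaves about 30, 35 and 36 of 45 for OS. For PFS, at assumed medians of 4-6 months, about 27-32 remain. If a further 10-20% of samples are late or missing (assumption), about 24-32 and 22-29 remain. The result then applies only to patients who reach the C3 assessment.

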1.3.8. To determine if APR-246 treatment upregulates p53 target genes

1.3.9. To determine if APR-246 induces reactive oxygen species (ROS) production

1.3.10. To determine the rate and time to acute myeloid leukemia (AML) transformation

1.3.11. To determine the median overall survival (OS)

1.3.12. To determine whether recurrent genetic mutations are predictive of response

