2. BACKGROUND

2.1. Myelodysplastic Syndromes

Myelodysplastic syndromes (MDS) are a heterogeneous group of neoplasms arising from a clonal hematopoietic precursor^{1,2}. MDS is characterized clinically by cytopenias and a tendency to transform to acute myeloid leukemia (AML)³. Prognostic scoring systems have been

developed to help stratify patients based on predicted survival and progression to AML³⁻⁵. In practice, treatment decisions are made by grouping patients with MDS into lower and higher risk subgroups as defined by clinical prognostic scoring systems. Specifically, the International Prognostic Scoring System (IPSS) and its more modern version, the revised-IPSS (RIPSS), represent the most widely used clinical prognostic tools^{3,4}. Those patients that fall in the higher risk group have an expected survival of less than 12 months if left untreated and progress to AML greater than 30% of the time.

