We have recently analyzed our own experience on molecularly profiled patients at Moffitt Cancer Center and identified that the clonal burden, or variant allele frequency (VAF), had significant impact on clinical phenotype and more importantly further stratified prognosis over binary mutational analysis alone and/or clinical prognostic models¹⁹. Specifically, MDS patients with a *TP53* VAF > 40% had a median overall survival (OS) of 124 days versus an OS that was not reached in patients with VAF < 20% (hazard ratio (HR), 3.52; $P = 0.01$) with validation in an independent cohort (HR, 4.94, $P = 0.01$). Overall, *TP53* mutant MDS and AML patients have a median OS ranging from 5-9 months with 8 months representing the best estimate when restricting to MDS and oligoblastic AML (20-30% blasts)^{9,19-22}. Together, these data highlight the dismal outcomes of *TP53* mutant patients and the dire need for the development of novel therapeutic strategies, particularly in this patient population.

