[REDACTED]

[REDACTED]

[REDACTED]

Other investigational therapies must not be used while the patient is on the study.

7. Duration of Therapy

Subjects will be treated for a total of 6 cycles. For subjects who have stable disease or better, treatment may continue until one of the following criteria applies:

- e. Inter-current illness that prevents further administration of treatment,
 - f. Unacceptable adverse event(s),
 - g. Patient decides to withdraw from the study, or
 - h. General or specific changes in the patient's condition render the patient unacceptable for further treatment in the judgment of the investigator.
- e. Evidence of disease progression by the IWG 2006 criteria, not applicable at bone marrow evaluation at day -10 of lead in phase.

Subjects who wish not to continue treatment will complete their end of study visit upon completion of cycle 6.

8. Duration of Follow-Up

Subjects will be followed as per calendar on treatment for 6 cycles. After 6 cycles, patients who continue on treatment will be followed monthly. Off treatment data on AML transformation and overall survival will be updated every 6 months or until death, whichever occurs first. Subjects removed from study for unacceptable adverse events will be followed until resolution or stabilization of the adverse event.

9. Criteria for Removal from Study

a. Subject Completion

A subject will be considered to have completed the study if the subject meets at least 1 of the following criteria:

- The subject has progressive disease.
- The subject died during the study.
- The subject experience a treatment related AE that led to withdrawal from the study.
- The subject starts new treatment for their underlying disease (MDS/CMML/AML).

b. Subject Withdrawal from Study

A subject may voluntarily withdraw from study medication or withdraw consent from the study at any time. The investigator may also, at his or her discretion, discontinue a subject from participating in the study at any time. The investigator and/or designated staff will record the date and the reason for subject withdrawal from the study.

c. Subject Withdrawal from Study Medication

If the subject is permanently withdrawn from treatment with study medication, but does not withdraw consent, the investigator must make every effort to have the subject complete all withdrawal assessments at the time of withdrawal, and complete all scheduled follow-up visits.

Treatment with study medication must be discontinued if:

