End of Cycle 6 Evaluation and End of Treatment: Subjects discontinuing treatment early should complete their end of treatment visit within approximately 28 days of their last dose of investigational product. Physical exam, vital signs, adverse event reporting, CBC, and blood chemistry and BM aspirate and biopsy with cytogenetic and NGS analysis should be performed if feasible.

Off Treatment assessment: includes best response, date of first response, date of loss of response, reason for discontinuation.

Off study CRF: vital status, date of death/last contact, transformation to AML and the date of transformation to AML if applicable.

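### Kaplan-Meier is the only method Section 15.4 gives for time-to-event endpoints; if it is applied to time to AML transformation with deaths censored, it overstates the incidence

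*Combined protocol and SAP*

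**What the plan says.** Section 1.3.10 sets the objective: "To determine the rate and time to acute myeloid leukemia (AML) transformation". The synopsis repeats it. Section 3.2.9 and item x of the list in Section 15.4 give the matching endpoint as "AML transformation according to World Health Organization (WHO) criteria", separate from OS (item xi) and LFS (item xii).

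After that list, Section 15.4 states the only method for this class: "Time-to-event endpoints such as OS and LFS will be summarized using the Kaplan-Meier product-limit method". For the secondary endpoints as a whole it says "Such data will be summarized appropriately in an exploratory fashion", with point estimates and 95% confidence intervals where feasible. Competing risks, cumulative incidence and the handling of a death without AML are not mentioned anywhere.

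The data for a better analysis are planned. Off-treatment follow-up in Section 13 records vital status, date of death or last contact, and "transformation to AML and the date of transformation to AML if applicable". Section 8 gives the frequency: "Off treatment data on AML transformation and overall survival will be updated every 6 months or until death, whichever occurs first".

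**The concern.** For OS, and for LFS in its usual sense (the documents do not define it), death is an event and Kaplan-Meier is the right estimator. For time to AML transformation, death without AML ends any chance of the event. Treating that death as censoring assumes that the patient could still have transformed at the same rate as the survivors.

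The competing event will be common here. Section 2.2 puts median OS in TP53-mutant MDS and AML at 5 to 9 months, with "8 months representing the best estimate when restricting to MDS and oligoblastic AML (20-30% blasts").

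At stake is the transformation rate that the trial reports. Section 15.4 expects these preliminary data to inform further study of the regimen. In a single-arm trial, an inflated rate would compare badly with historical rates that were computed as crude proportions or cumulative incidences, to the disadvantage of the regimen.

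**Working it through.** **Plan's own figure.** The documents state no expected transformation rate, so there is none to reproduce. The one design calculation they contain, the Simon rule (at least 6 of 24, then at least 14 of 45, for 20% against 40%), does reproduce: alpha 0.048, power 0.900, probability of early termination 0.656. It does not involve this endpoint.

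**Direction.** At each transformation time with r patients at risk and d transformations:
- one minus Kaplan-Meier rises by K × d/r, where K is the Kaplan-Meier curve with deaths censored;
- the Aalen-Johansen cumulative incidence rises by S × d/r, where S is the proportion still free of both AML and death.

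S is never above K, and falls below it after the first death without AML. So one minus Kaplan-Meier is never below the cumulative incidence, and exceeds it once a transformation follows such a death. No hazard assumption is needed.

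**Size: inputs.**
- Median time to the first of AML or death, m = 8 months. Assumption: the historical OS figure from Section 2.2 as a stand-in, because no LFS figure is given. Range 8 to 12 months.
- Share of first events that are AML, s = 30%. Assumption, prompted by Section 2.1, which says that higher-risk patients left untreated "progress to AML greater than 30% of the time". That is not a figure for treated TP53-mutant patients. Range 20% to 40%.
- Constant hazards, with total hazard λ = ln 2 / m.

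**Formulas.**
- Cumulative incidence: CIF(t) = s × (1 − exp(−λt)) = s × (1 − 2^(−t/m))
- Kaplan-Meier with deaths censored: 1 − KM(t) = 1 − exp(−sλt) = 1 − 2^(−st/m)

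**Central case (m = 8, s = 0.30).**
- 8 months: CIF = 0.30 × (1 − 2^(−1)) = 15.0%; 1 − KM = 1 − 2^(−0.3) = 18.8%
- 12 months: CIF = 0.30 × (1 − 2^(−1.5)) = 19.4%; 1 − KM = 1 − 2^(−0.45) = 26.8%
- 24 months: CIF = 0.30 × (1 − 2^(−3)) = 26.3%; 1 − KM = 1 − 2^(−0.9) = 46.4%

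**Range.** Excess in percentage points, from unrounded values:

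| Median (months) | AML share | 12 months: CIF / 1 − KM | Excess | 24 months: CIF / 1 − KM | Excess |
|---|---|---|---|---|---|
| 8 | 20% | 12.9% / 18.8% | 5.8 | 17.5% / 34.0% | 16.5 |
| 8 | 30% | 19.4% / 26.8% | 7.4 | 26.3% / 46.4% | 20.2 |
| 8 | 40% | 25.9% / 34.0% | 8.2 | 35.0% / 56.5% | 21.5 |
| 12 | 20% | 10.0% / 12.9% | 2.9 | 15.0% / 24.2% | 9.2 |
| 12 | 30% | 15.0% / 18.8% | 3.8 | 22.5% / 34.0% | 11.5 |
| 12 | 40% | 20.0% / 24.2% | 4.2 | 30.0% / 42.6% | 12.6 |

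The excess is therefore about 3 to 8 points at 12 months and 9 to 21 points at 24 months (the maximum is 21.47). Widening the inputs to shares of 20-50% and medians of 6-18 months gives 1.4 to 12.6 points at 12 months and 4.8 to 29.5 at 24 months.

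**Simulation check.** With 45 patients, 4,000 runs, the central hazards and uniform censoring between 12 and 36 months, mean estimates were 26.9% (1 − KM) against 19.4% (Aalen-Johansen) at 12 months, and 46.2% against 26.4% at 24 months. One minus Kaplan-Meier was never the smaller of the two.

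**Time to transformation.** In the central case the cumulative incidence levels off at 30%, so no median time to AML exists. One minus Kaplan-Meier would still reach 50%, at m/s = 8/0.30 = 26.7 months.

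**The case against.** **The plan does not assign Kaplan-Meier to this endpoint by name.** The sentence names OS and LFS, for which it is right. The endpoint is worded as an occurrence, and the provision for an appropriate exploratory summary leaves room for a crude proportion with an exact interval, which would not carry this bias. This stands in part. A reader might infer that the plan commits to the error and that the reported rate will be overstated; the documents support only the conditional statement. But OS and LFS are given as examples of a class, the objective asks for time as well as rate, and no other method is offered. A crude proportion would also ignore unequal follow-up and leave the time part of the objective unanswered.

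**The endpoint carries little weight.** It is one of 13 exploratory secondary analyses, LFS is reported as well, and no hypothesis, sample size or stopping rule uses it. This stands. A reader who infers that the trial's conclusion is at risk goes too far: that rests on the CR count.

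**The size is assumed.** This stands. The 8 months is historical OS, and the 30% comes from untreated higher-risk disease. The 24-month contrast is the most striking and the least secure: event-free patients would be 2^(−3) = 12.5% of 45, about 6, before other censoring. At 12 months the central excess of 7.4 points is smaller than the approximate 95% half-width, 1.96 × √(0.194 × 0.806 / 45), or about 12 points. That limits the practical weight, but it does not remove a bias that always runs one way.

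**One minus Kaplan-Meier is a defined quantity.** Correct: it is the net risk if death could be removed and censoring were independent. It would be wrong to call it meaningless. It is simply not the proportion of these patients who transform.

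**Conclusion.** The point holds as a conditional gap in the analysis plan. Time to AML transformation falls under the Kaplan-Meier sentence by class, with no alternative and no rule for death without AML. If that sentence is followed with deaths censored, the incidence is overstated. The direction needs no hazard assumption, only that some deaths without AML come before later transformations.

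The size does rest on assumptions: constant hazards, historical OS standing in for time to first event, and an assumed AML share. On these it is about 7 points at 12 months in the central case (range 3 to 8), and 9 to 21 points at 24 months, where few patients remain at risk. The change is worth making because it is cheap, but the CR analysis, the sample size and the two-stage rule do not depend on it.

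**What to change.** In Section 15.4, state that time to AML transformation is summarised by the cumulative incidence function (Aalen-Johansen estimator) with 95% confidence intervals, and with death without AML as a competing event. Keep Kaplan-Meier for OS, LFS and PFS.

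In the same place, state what counts as a transformation and who is at risk of it. Three parts of the protocol need to be reconciled:
- the endpoint uses WHO criteria (Sections 3.2.9 and 15.4), and the WHO table in Appendix C ends MDS at 19% marrow blasts;
- Appendix B defines transformation as 30% or more blasts;
- inclusion criterion 4 in Section 4.1 admits patients with AML and 20-30% blasts, who on the WHO reading have the event at entry.

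Until this is settled, the cumulative incidence curve is not fully specified either.

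The cost is a sentence for the method and a short paragraph for the definitions, which need clinical agreement. No visits, patients or data items are added: baseline marrow, date of transformation and date of death or last contact are already collected under Section 13, and off-treatment status is already updated every 6 months under Section 8.
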